5.4 Sample size justification

R0.6C is a phase 1 safety and efficacy trial in healthy volunteers, designed to identify safety concerns associated with R0.6C administration at different dosages and/or adjuvants. A total of 32 healthy adults (males and females) aged 18 – 55 will be divided over four groups. Each group will include eight subjects.

Sample size for each group is appropriate based on similar trial designs in malaria protein vaccination studies. This is a small Phase 1 study; therefore, it is largely descriptive and is intended to provide primarily safety data of 2 doses of R0.6C combined with 2 adjuvants. Comparative statistics will be performed but will have low power to detect anything other than very large differences between the groups.

Furthermore, if we assume an effect size of 75% TRA at 14 days after the fourth R0.6C vaccination (I4+I4) compared to baseline (I1-I1), with the subject size of n=8 per dose/adjuvant arm we will have an empirical power of >99%, based on calculations and assumptions as described below in paragraph 5.4.1.

5.4.1 Estimation of empirical power for an analysis of transmission reducing activity under different assumptions

The simulation algorithm

1. We generate n_0 subjects in the control (pre-treatment) group and n_1 subjects in the treatment (post-treatment) group with a variable x_i to indicate whether the subject is in the control group ($x_i = 0$) or in the treatment group ($x_i = 1$).
2. We generate m mosquito dissections for each subject.

3. We simulate subject-specific random intercepts (z_i) from a normal distribution with a mean of 0 and a specified standard deviation σ , i.e. $Z \sim N(0, \sigma)$.

4. Lastly we generate the oocyst counts (y_{ij}) for each subject i and mosquito j using a negative binomial distribution such that $Y \sim NB(\mu, \theta)$ where θ is the anticipated dispersion parameter and $\mu_{ij} = \exp(\beta_0 + \beta_1 x_{ij} + z_i)$ where β_0 is the anticipated mean of the log oocyte counts in the control group and β_1 is the anticipated regression coefficient used to estimate the TRA, such that

$$\beta_1 = \log\left(1 - \frac{TRA}{100}\right).$$

The model

To analyze the simulated data, we make the of the *mgcv* package in R. We run a Generalized Additive Mixed Model such that,

$$\log(y) = \beta_0 + \beta_1 x + z_i.$$

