From each simulated dataset, we estimate the $TRA = \left(1 - \exp(\hat{\beta}_1)\right) \times 100$ and p (the p-value) of the test for whether β_1 is significantly different from 0. We then report the average TRA across simulations, which should be close to the anticipated value, and the emperical power which we define as the percentage of p 's less than 0.05.

Simulation results

We chose $m = 20$ as the standard amount of mosquito dissections per subject. We used a previous study (NL69779.091.19) to extract anticipated values for the mean log oocyst count in the control group, the dispersion parameter θ and the standard deviation of the random effects σ . i.e. $\beta_0 = 3.7037$, $\theta = 4.451$ and $\sigma = 0.64$. For the anticipated TRA (and thus anticipated β_1) we used a range of assumed values, i.e. $TRA = (25\%, 50\%, 75\%)$. We also varied the number of people in the control and treatment groups, i.e. n_0 and n_1 . The tables below show the emperical power under these scenarios.

TRA = 25%		n_1				
n_0	5	6	7	8	9	10
10	17.0	18.4	17.4	18.4	18.2	19.0
11	17.2	15.8	16.6	17.6	19.6	19.4
12	17.0	17.6	18.2	18.4	19.4	19.2
13	17.2	16.4	17.6	17.4	20.6	19.6
14	16.6	17.8	19.8	20.2	19.4	20.2
15	15.4	17.4	18.8	19.4	20.8	22.6
16	14.6	15.2	17.8	19.8	20.4	21.0
17	14.4	15.8	18.6	19.0	20.6	22.4
18	14.4	16.2	18.2	18.8	21.0	22.6
19	17.4	19.0	18.6	19.4	22.2	24.8
20	15.8	17.8	19.4	22.2	25.8	26.8

TRA TRA = 50%	n₁					
	n₀	5	6	7	8	9
10	52.0	57.0	60.4	63.8	64.4	67.0
11	54.2	58.8	62.4	63.8	65.2	69.6
12	55.0	59.4	62.8	65.4	69.2	70.6
13	54.6	58.2	63.6	67.0	69.4	71.8
14	58.4	62.4	64.8	68.2	70.4	73.0
15	55.6	59.2	65.0	66.6	70.4	74.0
16	55.2	60.4	64.0	68.0	71.6	75.8
17	54.6	60.6	66.8	69.8	75.8	78.2
18	54.2	61.6	67.8	72.2	75.6	78.4
19	59.6	66.8	71.0	76.8	78.8	81.6
20	61.8	68.2	72.8	78.6	80.6	82.8

TRA = 75%	n₁					
	n₀	5	6	7	8	9
10	97.2	99.0	99.6	99.8	99.8	100.0
11	98.2	99.6	99.8	99.6	99.6	100.0
12	98.4	99.2	99.2	99.8	100.0	100.0
13	97.4	99.0	99.6	99.8	100.0	100.0
14	96.6	98.8	99.2	99.8	100.0	100.0
15	97.8	99.2	99.8	100.0	100.0	100.0
16	98.4	98.8	99.6	99.8	100.0	99.8
17	99.4	99.8	100.0	100.0	100.0	100.0
18	99.0	100.0	100.0	99.8	100.0	100.0
19	99.2	99.6	99.6	100.0	100.0	100.0
20	99.0	99.2	99.8	100.0	100.0	100.0

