### Sample size

STOP-TRANS is an exploratory first-in-human study with the objective to identify large safety and tolerability signals. In addition, SMFAs are done to provide a first proof-of-concept. The study is largely descriptive and is intended to provide primarily safety data of 2 dose levels of R0.6C combined with 1 or 2 adjuvants given 4 times over 24 weeks. Comparative statistics will be performed but will have low power to detect anything other than very large differences between the groups. In total 32 participants will receive R0.6C. Based on a binomial distribution, this means that the probability to detect at least one clinically significant event (e.g. a serious adverse reaction) during vaccination with a power of 90% is 7%.

Furthermore, if we assume an effect size of 75% TRA at 14 days after the fourth R0.6C vaccination (I4+I4) compared to baseline (I1-I1), with the subject size of  $n=8$  per dose/adjuvant arm we will have an empirical power of >99% ( $\alpha=0.05$ ) to detect this, based on calculations and assumptions as described in the next paragraph.

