## Statistical Principles

### Confidence intervals and P values

Two-sided p values less than 0.05 will be considered statistically significant. Adjustments for multiple comparisons will be implemented where appropriate.

Where applicable, normally distributed continuous outcomes will be presented as mean with 95% CI or standard deviations. Continuous outcomes that are not normally distributed will be transformed using a suitable transformation before reporting 95% CIs or will be presented with median and interquartile ranges. For discrete (or count) data we will find interquartile ranges. Binary data will be presented as counts and proportions.

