### Efficacy outcome analyses

- Pfs48/45-6C and R0.6C antibody prevalence and density will be determined by ELISA; the mean of duplicate concentration estimates is used for analyses. Antibody density will be expressed in  $\mu\text{g/mL}$  using humanized monoclonal antibody TB31F as a reference/standard. (Endpoint 5, 7 and 11).
- The R0 antibody prevalence and density will be determined by ELISA; the mean of duplicate concentration estimates is used for analyses. Antibody density will be expressed in  $\mu\text{g/mL}$  using R0 monoclonal antibody as a reference/standard. Alternatively, R0 antibody densities may be expressed in arbitrary units (AU) or R0 antibody densities may be estimated by subtracting measured R0 antibody levels from R0.6C antibody levels. (Endpoint 8).
- Pfs48/45-6C antibody density will be plotted over time per individual and either as a mean or geometric mean per group. AUC and mixed effects models may be used to investigate the effect of timepoints, dose/adjuvant group and their interactions on the 6C antibody concentration. Mixed models use specific random intercepts to control for the correlation within individuals (Endpoint 7).

- TRA will be quantified as the relative reduction in oocyst intensity for test samples (one feeder per test sample) compared to baseline serum controls. Samples may be tested in one or two independent SMFA experiments. If significant transmission reduction is measured, TRA values for each participant and time-point will be estimated using generalized linear models, as previously described. (Endpoint 2, 4 and 10).
- We may calculate the percentage of individuals per group that have at least 50%, 80% and 90% TRA at relevant timepoints and the percentage of individuals per group with statistically significant TRA at relevant timepoints. Mean TRA levels may also be calculated per study group per time point and compared between groups. (Endpoint 10).
- Modeled TRA estimates (based on antibody concentration) may be plotted against observed TRA estimates.
- TBA will be quantified as the reduction in oocyst prevalence in the presence of test serum as compared to (pooled) baseline serum^1 and presented per group and time-point. (Endpoint 6).

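### For the exploratory, randomised adjuvant comparison of TRA, adjusting for each subject's own baseline oocyst density would be a cheap gain in precision; the SAP names no covariate

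*SAP*

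**What the plan says.** The SAP's Efficacy outcome analyses define the measure for Endpoints 2, 4 and 10 together: "TRA will be quantified as the relative reduction in oocyst intensity for test samples (one feeder per test sample) compared to baseline serum controls". If significant reduction is seen, generalized linear models then give a value for each participant and time point. For Endpoint 10, the difference between dose groups and/or adjuvant groups, the SAP adds: "Mean TRA levels may also be calculated per study group per time point and compared between groups". It names no test, scale or covariate for that comparison.

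Four other places bear on the point:

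- Protocol section 10 says the SAP will state which covariates or factors any adjusted analyses include. The SAP names none for TRA.
- The notes to the schedule in protocol section 8.3.17 list I1-1 among the three minimum SMFA time points, so a baseline assay is planned.
- Protocol section 8.2 lets volunteers choose their dose group and randomises only the adjuvant, within each enrolment group.
- Protocol section 5.4 and the SAP's Sample size section both say that between-group comparisons have low power.

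**The concern.** When a subject's TRA uses that subject's own baseline and is analysed on the log scale, comparing TRA between groups is a change-score analysis: log post minus log baseline, with the baseline coefficient fixed at 1. All the noise in the baseline reading then enters the compared quantity. Estimating the coefficient instead of fixing it removes part of that noise unless pre and post readings are very highly correlated.

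What is at stake is precision in one exploratory comparison. The adjuvant contrast is the only randomised contrast in the trial and is already acknowledged to be weakly powered. The primary endpoint compares I4+14 with baseline within each group and is untouched.

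**Working it through.** **Inputs from the documents.**
- Significance: "Two-sided p values less than 0.05 will be considered statistically significant" (SAP, Confidence intervals and P values).
- Group size: "Each group will include eight subjects" (protocol 5.4). The adjuvant contrast is therefore 8 v 8 within a dose, or 16 v 16 over both doses.
- Simulation parameters (protocol 5.4.1 and SAP): mean log oocyst count 3.7037, dispersion 4.451, between-subject SD (sigma) 0.64, and 20 mosquitoes "as the standard amount of mosquito dissections per subject".

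**Assumptions not in the documents.** Rho, shown from 0 to 0.9. A between-group effect of TRA 50% v 75%, a difference of ln(0.50/0.25) = ln 2 = 0.693 in log density.

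**Step 1: reproduce the plan's own figure.** The SAP reports power above 99% "if we assume an effect size of 75% TRA at 14 days after the fourth R0.6C vaccination". On the log scale 75% TRA is ln 4 = 1.386, and power = Φ(1.386 / (0.64·√(1/n0 + 1/n1)) − 1.96).
- 10 v 8: Φ(1.386/0.3036 − 1.96) = Φ(2.61) = 99.5%; the table gives 99.8%.
- 8 v 8, not tabulated: Φ(1.386/0.32 − 1.96) = Φ(2.37) = 99.1%.
- 50% TRA, 10 v 8: 62.7%; the table gives 63.8%.

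The log-scale approximation with SD 0.64 matches the plan's simulation. No power is stated for Endpoint 10.

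**Step 2: variance of the compared quantity, same effect in every subject.**
- Log ratio to own baseline: 2·sigma²·(1 − rho)
- Baseline as covariate: sigma²·(1 − rho²)
- Covariate variance over ratio variance: (1 + rho)/2, which is 0.75 at rho 0.5.

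**Step 3: normal approximation at rho 0.5.** The SDs are 0.64·√1 = 0.640 (ratio) and 0.64·√0.75 = 0.554 (covariate).
- 16 v 16: Φ(0.693/0.2263 − 1.96) = 86.5%, against Φ(0.693/0.1960 − 1.96) = 94.3%.
- 8 v 8: Φ(0.693/0.320 − 1.96) = 58.2%, against Φ(0.693/0.277 − 1.96) = 70.6%.

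**Step 4: simulation.** This used negative binomial counts with the plan's parameters, and compared a t-test on the log ratio with ANCOVA. It allows for mosquito noise, small-sample t-tests and estimation of the slope. Repeat runs agree within about 2 points.

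| rho | 8 v 8: ratio → covariate | 16 v 16: ratio → covariate |
|---|---|---|
| 0 | 29% → 48% | 54% → 80% |
| 0.5 | 49% → 59% | 83% → 91% |
| 0.7 | 70% → 74% | 96% → 98% |
| 0.9 | 97% → 96% | 100% → 100% |

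The size also depends on the effect. By normal approximation at rho 0.5, the gain runs from 0.2 points (3-fold difference, 16 v 16) to 12.4 points (2-fold, 8 v 8).

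**Step 5: vaccine effect varying between subjects.** With an assumed SD of 0.64 on the log scale, sigma² is added to both variances. At rho 0.5 these become 2·sigma² and 1.75·sigma², a ratio of 0.875 instead of 0.75. The simulated gain falls to about 2 points at 8 v 8 and 4 at 16 v 16.

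**Step 6: groups that differ at baseline.** Suppose there is no true difference in TRA but one group's densities are higher both before and after. The ratio cancels the shift. ANCOVA with slope near 0.5 removes only about half of it. Simulated type I error at rho 0.5:

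| Shift | Ratio | Covariate, 8 v 8 | Covariate, 16 v 16 |
|---|---|---|---|
| none | about 5% | about 5% | about 5% |
| 1.5-fold | about 5% | about 10% | about 16% |
| 2-fold | about 5% | about 18% | about 31% |

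**The case against.** The strongest reply is that the SAP does not commit to the analysis used here as comparator. It says groups may be compared and names no test or scale, and the cited modelling method and online tool cannot be inspected. That stands. A reader might infer that the SAP forces a baseline coefficient of 1; this is true only on the log scale and with the subject's own baseline. For TRA the SAP says baseline serum controls, and the wording "as compared to (pooled) baseline serum" appears only for TBA. Own baseline is the better-supported reading, because TRA is estimated per participant and protocol 10.1 calls for paired pre-post tests, but it should be stated. With a pooled baseline the coefficient would be 0, and individual baseline densities might not exist.

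A reader might also infer that the baseline reading comes from a single feeder. The SAP says this of test samples only.

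Nor should rho be read off the plan. Its simulation generates pre and post as separate groups of unequal size, which is a simplification and not evidence that rho is 0. The subjects are malaria-naive, so any correlation may largely reflect shared assay conditions and could be high, where the gain disappears.

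Finally, adjustment can do harm where groups are not randomised. Step 6 bears this out, and it limits the recommendation to the adjuvant contrast. Even there, an assay shift could enter if the two arms were run in different experiments.

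**Conclusion.** This is a worthwhile, low-cost improvement to an optional exploratory analysis, not an error. For the adjuvant contrast, using the I1-1 density as a covariate gains roughly 8 to 10 points of power at rho 0.5, more at lower rho, and nothing at rho 0.9. Those figures assume TRA 50% v 75% and a common effect. If the effect varies between subjects with SD 0.64, the gain at rho 0.5 is about 2 to 4 points. Rho, the effect size and the common effect are all assumptions.

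Two stronger conclusions are tempting and not supported. One is a general gain of about 8 points: that holds for particular values of rho, effect and group size. The other is that every Endpoint 10 contrast should be covariate-adjusted: dose is self-selected, and adjustment there could inflate false positives.

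**What to change.** In the SAP, before database lock:

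1. State that TRA uses the subject's own I1-1 serum as comparator.
2. For the adjuvant contrast, model I4+14 oocyst density on the log scale, for example with a negative binomial or other log-link model, which tolerates zero counts. Include the subject's own log I1-1 density as covariate, and enrolment/dose group and SMFA experiment as factors. Report the ratio of adjusted densities with a 95% CI.
3. Test both adjuvant arms in the same SMFA experiments.
4. For the dose contrast, keep the ratio to baseline as the main comparison and say why.
5. Keep individual TRA values for description.

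The cost is SAP wording and some planning of assay runs, with no new visits or samples if each subject's I1-1 serum is fed individually. The covariate uses one degree of freedom and loses about 1 to 2 points of power at 8 v 8 if rho is about 0.9.
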